During analysis of the baseline data, we found that the DI (i.e. sensitivity x secretion) is sometimes paradoxically lower in pediatric participants than adult participants, despite the fact that the insulin sensitivity vs. C-peptide curves describing the relationship between these two variables appears higher in children. This contradictory finding is at least in part due to the fact that the range of values for insulin sensitivity among children is narrow compared to that of adults, i.e., children are more insulin resistant than adults. Further, the log-log slopes of insulin sensitivity vs. C-peptide responses are not equal to -1 in children or adults (or overall). Although the untransformed data show a clear inverse relationship typical of a hyperbolic curve, the slopes for each of the primary outcome measures on the log scale is approximately -0.3 (not -1.0 as may have been expected); this is a hyperbola but not a square hyperbola. Thus, the approach of performing the primary outcome analysis comparing treatment groups after washout, with a test of difference in DI at Month 15 adjusted for baseline, may not be appropriate and needed to be reassessed.

Several options were considered including a simple linear regression model (on a log scale) of C-peptide (and insulin) release as a function of insulin sensitivity, with a term for treatment group and adjusting for both variables at baseline. However, this was also deemed inappropriate because that model would estimate the difference in C-peptide (and insulin) release between groups assuming that there was no difference in insulin sensitivity between groups. Rather, we want to account for movement of both variables simultaneously without forcing a specific relationship between them. This can be accomplished by performing the primary outcome analysis using two separate models: insulin sensitivity at Month 15 vs. treatment arm (adjusted for baseline) and C-peptide (and insulin)

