release at Month 15 vs. treatment arm (adjusted for baseline), where the two models are fit simultaneously using Seemingly Unrelated Regression techniques¹⁻⁵. This provides an estimate of the treatment group difference in insulin sensitivity as well as the treatment group difference in the release of the beta-cell peptides, while allowing for the correlation among the insulin sensitivity and peptide release measures. This yields an estimate of the joint covariance structure of the two models, and allows a joint statistical test of both variables using a 2-DF chi-square test of the treatment arm difference in each model. Thus, we will be able to test whether both the insulin sensitivity and C-peptide (and insulin) release variables are different across treatment groups at Month 15, adjusted for their baseline value.

This approach will provide a clear answer to the question of whether the Month 15 result differs by treatment, adjusting for baseline measures. However, given that an underlying reciprocal relationship is expected, it is possible that a significant difference could be found between groups, but that this represents a proportional shift without a specific improvement in peptide release adjusted for sensitivity. In other words, the data points could lie on a different part of a shared relationship curve such that the change represents a mutually compensated change in these terms without a separate underlying change in beta-cell function. Therefore, if the results of the two model analysis are significant, further analysis will evaluate the patterns of change in either or both variables within each group.

Below is sample Primary Outcome R code for this primary analysis.

R code and sample output for primary outcome with Seemingly Unrelated Regression model using systemfit

```
> fit12=systemfit(list(Eq1 = log_mi ~ Treatment + log_mi_base,
  Eq2 = log_cpeptide_steady ~ Treatment +
  log_cpeptide_steady_base),
  method='SUR',
  data=RISEM15)

> linearHypothesis(fit12,test = "Chisq",
  c('Eq1_TreatmentTreat2=0','Eq2_TreatmentTreat2=0'))

Hypothesis: Eq1_TreatmentTreat2 = 0      Eq2_TreatmentTreat2 = 0

Model 1: restricted model
Model 2: fit12

  Res.Df   Df   Chisq     Pr(>Chisq)
1    xxx
2  xxx-2   2   xxxx   x.xxx ← pvalue for the 2-DF joint statistical test
of both sensitivity and secretion variables of the treatment arm
difference
```

References:

1. https://en.wikipedia.org/wiki/Seemingly_unrelated_regressions

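### The 2-df test can show only that insulin sensitivity or C-peptide differs, not that both do, and the only follow-up the SAP names for a compensated shift is within-group

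*SAP*

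**What the plan says.** Protocol 3.2 names two co-primary outcomes, the steady-state and the arginine-stimulated C-peptide responses. Each is adjusted for clamp-derived insulin sensitivity (M/I), and each treatment is compared with placebo after the 3-month washout.

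The SAP drops the disposition index (DI) because, at baseline, "the slopes for each of the primary outcome measures on the log scale is approximately -0.3" and not -1. It also rejects a regression of C-peptide on sensitivity, giving as its aim: "we want to account for movement of both variables simultaneously without forcing a specific relationship between them". It fits instead one equation for log M/I and one for log C-peptide, each adjusted for its own baseline, which "allows a joint statistical test of both variables using a 2-DF chi-square test of the treatment arm difference in each model". The sample code sets the treatment coefficient to zero in both equations at once. The SAP then states the inference: "we will be able to test whether both the insulin sensitivity and C-peptide (and insulin) release variables are different across treatment groups". The fit also gives "an estimate of the treatment group difference in insulin sensitivity as well as the treatment group difference in the release".

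The SAP acknowledges a limit. It writes that, "given that an underlying reciprocal relationship is expected", a significant difference may be "a mutually compensated change in these terms without a separate underlying change in beta-cell function". Its response to a significant result is that "further analysis will evaluate the patterns of change in either or both variables within each group".

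**The concern.** There are two separate faults.

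The first is the stated meaning of the test. Rejecting a null that two coefficients are both zero supports the statement that at least one is non-zero. It does not show that both are.

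The second is the follow-up. The protocol's question concerns secretion relative to sensitivity, in each active arm against placebo. The SAP sets aside the two between-arm analyses that combined the variables and concedes that the joint test cannot by itself tell compensation from a change in β-cell function. It then turns to change within arms. Placebo participants can also change over 15 months: Protocol 3.1 includes that arm to show natural history, and Protocol 3.4.1 gives everyone lifestyle instruction. Change within one arm therefore does not isolate a treatment effect.

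At stake is how a significant primary result is read. If M/I rises and C-peptide falls against placebo, the plan states no between-arm analysis for judging whether that is compensation, gain or loss.

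**Working it through.** **1. The plan's own figure.** Table 3 gives 81% power at effect size 0.60, correlation 0.57 and 56 per arm. Simulating the closed test with the other two arms at placebo level gives 82.9%, and a pairwise t-test at two-sided α = 0.025 gives 81.5%, so the figure reproduces. The SAP says the power calculations were based on the DI, so 81% does not describe the 2-df SUR test. The documents give no figure for that test.

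**2. Inputs.** From the documents: n = 56 per arm and r = 0.57 (Protocol 9.3), and log-log slope about -0.3 (SAP). The r is borrowed from the DI-based calculation. Assumed, because the documents give no values: SD of log M/I 0.6, SD of log C-peptide given M/I 0.3, residual slope -0.3.

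Baseline adjustment multiplies SDs by √(1 - 0.57²) = 0.822:
- residual SD of log M/I: 0.6 × 0.822 = 0.493
- residual SD of secretion adjusted for M/I: 0.3 × 0.822 = 0.246
- residual SD of log C-peptide: √((0.3 × 0.493)² + 0.246²) = 0.287
- residual correlation: -0.3 × 0.493 / 0.287 = -0.51

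**3. What rejection shows.** The pairwise non-centrality is λ = (n/2) δ′Σ⁻¹δ. If only M/I differs, by 0.60 residual SD, then λ = 28 × 0.36 / (1 - ρ²). For ρ = -0.3, -0.5 and -0.7, λ is 11.1, 13.4 and 19.8. The 2-df test rejects in 86%, 92% and 98%. In simulation, both components are individually significant in only 3% to 5% of trials.

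**4. Fully compensated shift.** Let M/I move by k residual SDs and C-peptide follow the -0.3 slope exactly. Under these assumptions λ = 28k², and the 5% critical value is 5.99.

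| k | M/I | C-peptide | λ | Significant |
|---|---|---|---|---|
| 0.3 | +16% | -4.3% | 2.52 | 28% |
| 0.4 | +22% | -5.7% | 4.48 | 46% |
| 0.5 | +28% | -7.1% | 7.00 | 66% |
| 0.6 | +34% | -8.5% | 10.08 | 82% |

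Actual two-equation SUR fits (2,000 runs) gave 81% at k = 0.6. Varying the residual SD ratio of C-peptide to M/I from 0.5 to 1.0 and ρ from -0.3 to -0.7 gives 28% to 35% at k = 0.3 and 82% to 92% at k = 0.6.

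**5. Signs alone do not settle it.** Hold M/I at +34% (0.296 log units). A gain or loss of 0.3 SD in adjusted secretion is 0.3 × 0.246 = 0.074 log units.

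| True state | C-peptide | 2-df significant | Estimates show M/I up, C-peptide down |
|---|---|---|---|
| Compensation | -8.5% | 82% | 95% |
| Gain | -1.5% | 90% | 61% |
| Loss | -15% | 90% | over 99% |

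The between-arm contrast [difference in log C-peptide] + 0.3 × [difference in log M/I] has expected values 0, +0.074 and -0.074. If the slope is right, its 1-df test rejects a compensated shift at the nominal 5%. Its standard error is 0.246 × √(2/56) = 0.047, so the 95% half-width is 1.96 × 0.047 = 0.09. It addresses the right question, but would not reliably show an effect of this size.

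**The case against.** The best defence is that the SAP already sees the problem. It discloses the compensated-shift reading, the fit supplies signed between-arm differences, and *both* may be loose wording for *jointly*. All of that is fair, and when the two variables move the same way the signs can be read directly. But the sentence defines what the primary test shows, so it should be exact. Disclosing an ambiguity and then naming a non-randomised step leaves the protocol's question open.

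A second defence is that Protocol 3.3.1 and 9.2 plan between-arm analyses of related sensitivity-adjusted measures, such as the first-phase disposition index, insulin-based AIRmax and the oral disposition index. These are useful randomised evidence. They are not named as the follow-up to the SUR test, and they do not cover the two co-primary C-peptide responses.

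A third is that any contrast with a slope brings back a relationship the SAP chose not to force. This stands as a limit. The slope of about -0.3 is cross-sectional and need not be the path along which treatment moves people. The contrast should therefore be supporting only.

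A reader might infer more than the documents support:
- *That the 2-df test is invalid or inflates type I error.* It is valid for its null; simulated size under the joint null was 4.5% to 5.3%.
- *That the sponsor overlooked compensation.* The SAP states it.
- *That a formal benefit rule across a range of slopes is required.* No such range has a source in the documents, and imposing one on every result would conflict with the SAP's stated reasoning and cost power.
- *That the interpretation will be chosen to suit the data.* The documents show a missing step, not an intention.

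**Conclusion.** The point stands, and it is worth fixing before Month 15 results by arm are seen. The two textual faults need no numerical assumption: the inference is worded as *both* when the test supports *at least one*, and the only named follow-up is within-group when the question is between-arm.

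The 28% to 82% range is an illustration. It rests on assumed SDs and residual slope and on a correlation borrowed from the DI calculation, and it refers to single pairwise tests. It shows that significance alone is not evidence of a β-cell benefit in a proof-of-principle trial whose purpose is to find one.

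**What to change.** (a) In the SAP, replace the statement that both variables are different with *at least one of the two differs*, and add that significance alone is not evidence of improved β-cell function.

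(b) Replace the within-group follow-up with a between-arm one from the same SUR fit, for each C-peptide response and each comparison with placebo:
- Report both signed differences with 95% CIs, and their joint 95% confidence region drawn against the baseline curve. These estimates assume no slope.
- As a supporting sensitivity analysis, report [difference in log C-peptide] - b × [difference in log M/I] with its 95% CI. Give it at the adult baseline slope for that response (about -0.3, with its sampling error carried) and over a slope range fixed and justified before Month 15 results by arm are seen.
- State whether the conclusion depends on the slope.

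Within-group patterns may stay as description.

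The cost is SAP wording and linear combinations from a model already fitted, with no new data. The primary 2-df test still forces no slope. The downside is that the supporting contrast depends on an assumed slope, and some results will have to be reported as slope-dependent.

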**CONFIDENTIAL**

interest at the end of the intervention phase (12-months) and at 3-months and 9-months post-washout. As for the primary outcomes, all analyses will be adjusted for the baseline value of each outcome and will use the closed testing procedure described above to preserve an overall  $\alpha=0.05$  for those outcomes as well.

An important secondary analysis of this study is to determine whether  $\beta$ - and  $\alpha$ -cell function from OGTT and fasting samples are sufficiently well correlated with more robust assessments of  $\beta$ - and  $\alpha$ -cell function obtained from the hyperglycemic clamp to validate their use in large clinical trials. For these analyses, Pearson and non-parametric Spearman correlations of simple versus sophisticated measures of  $\beta$ - and  $\alpha$ -cell function will be computed. Correlations will be assessed for measures made both on and off therapy.

Finally, to examine biomarker associations with glucose metabolism, Pearson and non-parametric Spearman correlations of each biomarker with  $\beta$ - and  $\alpha$ -cell function, insulin sensitivity and glucose tolerance measures will be determined. In addition, multiple linear regression models will be developed to predict measures of glucose metabolism with the most informative biomarker sets.

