### **9.3 Sample Size/Power Calculations**

There is little preliminary data on the expected differences in the primary outcomes in previously drug-naïve patients following a washout. Several unpublished analyses provided ranges of possible differences between treated and placebo patients, as well as expected correlations between baseline and follow up measures. Therefore, sample size was based on a minimum effect size (i.e., absolute difference between any two groups divided by the standard deviation (SD)) using a two-sided significance level of  $\alpha=0.05$ , and a conservative correlation of 0.57 between baseline and follow up measures. A sample size of 56 per arm (224 total) at the end of the washout provides  $\geq 80\%$  power to detect a minimum effect size of 0.60 between any two treatment groups in either of the primary outcome measurements (see Table 3) for the closed-testing procedure as described above using a baseline-adjusted analysis of covariance. A higher effect size will result in significantly increased power. A total of 255 participants will be recruited to allow for a 10% loss to follow-up over the course of the study.

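### Each equation of the primary model adjusts only for its own baseline; pre-specifying both baseline clamp measures in both equations costs very little and may gain precision

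*SAP*

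**What the plan says.** The SAP's sample R code fits two equations jointly by Seemingly Unrelated Regression (SUR). The first is "fit12=systemfit(list(Eq1 = log_mi ~ Treatment + log_mi_base", so baseline log M/I is its only covariate besides treatment. The second is "Eq2 = log_cpeptide_steady ~ Treatment" with the single covariate "log_cpeptide_steady_base". The SAP text matches the code: both variables are tested "adjusted for their baseline value". Protocol section 9.2, which says it follows the approach for the primary outcomes, states that "all analyses will be adjusted for the baseline value of each outcome". Inference is by a Wald test that "allows a joint statistical test of both variables using a 2-DF chi-square test of the treatment arm difference in each model".

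The SAP considered one model that held both baselines: a single regression of peptide release on insulin sensitivity, "with a term for treatment group and adjusting for both variables at baseline". It rejected that model because it would compare secretion between arms as if sensitivity did not differ between them. That reason does not concern the second baseline. Neither document explains why the other baseline is left out of each SUR equation, or reports having examined it.

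**The concern.** The two clamp measures are inversely related at baseline; the SAP reports a log-log slope of about -0.3. If each is measured with error, baseline M/I may still help to predict Month 15 C-peptide after baseline C-peptide has been used, and the reverse. Leaving it out sets those cross-baseline coefficients to zero. If they are not zero, some explainable variance stays in the residual, and the arm contrasts are less precise than the collected data allow. The plan expects 56 evaluable participants per arm, so cheap precision is worth having.

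**Working it through.** **Inputs from the documents.** 56 per arm, 224 in total; adjusted effect size 0.60; own-baseline correlation r = 0.57 (Protocol section 9.3 and Table 3), "using a two-sided significance level of" 0.05. The SAP says the power calculations were for the disposition index, so 0.57 is borrowed here for log M/I and log C-peptide.

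**Assumed, because not given.** The correlation c between M/I and C-peptide at one visit (taken as equal at baseline and Month 15), and the cross-lag correlation l between one measure at baseline and the other at Month 15. The reported -0.3 is a slope, not a correlation.

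**The plan's own figure.** Table 3 gives 81% at effect size 0.60. An overall four-group test with equally spaced means (spacing assumed) has noncentrality 56 × 0.60² × 5/9 = 11.2. With 3 and 219 df this gives 80.4%. Using 0.5/√(1 − 0.57²) = 0.6085 as the effect size gives 81.6%. The stated 81% is reproduced, but for the disposition-index analysis. No power is stated for the SUR model.

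**Cost.** Residual df fall from 224 − 4 − 1 = 219 to 218. The residual sum of squares of a least-squares fit cannot rise when a covariate is added. The df-corrected variance can rise by at most 219/218 − 1 = 0.46%. In simulations with no partial value (6,000 trials per setting) it rose in about 68 to 69% of trials, and the mean standard error rose by about 0.3%.

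**Gain, with unit-variance measures.**

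- Partial R² of the other baseline = (l − rc)² / [(1 − r²)(1 − c²)]. It is zero when l = 0.57c.
- Planned SUR: the one-step slope is s = (vr − wl)/(v − wc), with v = 1 − r² and w = c − 2rl + r²c. Residual variance is then 1 − 2sr + s², and covariance is c(1 + s²) − 2sl.
- Both baselines: own slope b = (r − cl)/(1 − c²), cross slope g = (l − rc)/(1 − c²). Residual variance is 1 − br − gl, and covariance is c − bl − gr.
- Power of the 2-DF test: assume a C-peptide effect of 0.60 × √(1 − 0.57²) = 0.493 SD and none on M/I. Noncentrality is 28 × 0.493² × V/(V² − W²), where V and W are the residual variance and covariance, referred to chi-square on 2 df (critical value 5.99).

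Worked case, c = l = -0.3:

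- Partial R² = (-0.3 + 0.171)²/(0.6751 × 0.91) = 2.7%.
- Planned SUR: s = 0.559, V = 0.6752, W = -0.0583, noncentrality 10.15, power 82.2%.
- Both baselines: b = 0.5275, g = -0.1418, V = 0.6568, W = -0.0610, noncentrality 10.45, power 83.3%.

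| c | l | Partial R² | Variance, planned → both | 2-DF power, planned → both |
|---|---|---|---|---|
| -0.3 | -0.171 | 0 | 0.675 → 0.675 | 85.5% → 85.5% |
| -0.3 | -0.3 | 2.7% | 0.675 → 0.657 | 82.2% → 83.3% |
| -0.5 | -0.285 | 0 | 0.675 → 0.675 | 91.7% → 91.7% |
| -0.5 | -0.392 | 2.3% | 0.677 → 0.660 | 86.3% → 87.3% |
| -0.5 | -0.5 | 9.1% | 0.676 → 0.613 | 82.8% → 87.0% |

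Where l = c, variance falls by 1 − 0.6568/0.6752 = 2.7% and 1 − 0.6135/0.6761 = 9.3%. Simulated power agrees: 82.7% → 83.4% at -0.3 and 83.2% → 87.3% at -0.5. Type I error of the 2-DF test was 0.048 to 0.056 with either model.

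With the same covariates in both equations, SUR coefficients equalled equation-by-equation least squares (difference below 1e-14).

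**The case against.** The strongest reply is that nothing is wrong. Own-baseline adjustment is the stated plan in both documents, the code follows it, and randomisation keeps the arm contrasts consistent. The gain is conditional on correlations that nobody has reported, and it may be zero. All of that stands. The rejected one-equation model also gives little support: it used both baselines because Month 15 sensitivity was itself a predictor, so it does not show that the authors thought the second baseline belonged in each separate equation.

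Three stronger readings are tempting and are not supported.

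- A reader might infer that the omission biases the comparison or leaves chance imbalance uncorrected. Such imbalance is part of the sampling variance that the test already allows for; this is the same efficiency point in other words.
- A reader might infer that SUR with unequal covariates harms the planned test, because its slopes move away from the least-squares values. In the cases where l = c, its residual variance is 0.6752 and 0.6761 against 0.6751 for own-baseline ANCOVA. Its joint power is no lower: 82.2% against 82.1%, and 82.8% against 82.6%.
- A reader might call the extra covariate free. It is not quite: it uses one degree of freedom per equation.

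**Conclusion.** The planned model is valid, and the suggestion is optional. What holds is that a baseline measure already in hand is left out of each equation without a stated reason, and that the trade-off favours including it. The possible loss is about 0.5% in df-corrected variance. The possible gain is about 3 to 9% in residual variance and 1 to 4 points of 2-DF power.

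Those gains assume an own-baseline correlation of 0.57, equal cross-sectional and cross-lag correlations between -0.3 and -0.5, and an effect on C-peptide alone. With a cross-lag correlation of 0.57 times the cross-sectional one, there is no gain. The documents do not say where in that range the trial lies.

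**What to change.** Before unblinding, pre-specify the same covariates in both equations:

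- `Eq1 = log_mi ~ Treatment + log_mi_base + log_cpeptide_steady_base`
- `Eq2 = log_cpeptide_steady ~ Treatment + log_mi_base + log_cpeptide_steady_base`

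Use the same pair for the arginine-stimulated C-peptide outcome, with its own baseline in place of the steady-state one. The 2-DF joint test keeps its form, and the coefficients become those of ordinary ANCOVA in each equation. Both measures come from the baseline clamp, so no new data are needed. The change is one term per equation and a sentence in the SAP. If arm comparisons have already been seen, report it only as a labelled sensitivity analysis.

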**CONFIDENTIAL**

## ***9.1 Primary Outcome and Analyses***

Two primary outcomes each measuring  $\beta$ -cell function after 3-months of washout will be assessed for this trial. In order to maintain a study-wide  $\alpha=0.05$ , a closed testing procedure will be used to assess the primary outcome [89]. The closed testing procedure is a method of hierarchical testing which tests higher-order comparisons before allowing lower-level comparisons, thus controlling the type I error and preserving power. First,  $\beta$ -cell function will be compared across the four treatment groups using an analysis of covariance model adjusted for baseline  $\beta$ -cell function. From this model, the overall test of equality across the four treatment groups will be computed. If that overall test is significant at the  $\alpha=0.05$  level, then each of the four possible sets of three interventions will be compared in four separate analysis of covariance models. The final significance testing of any set of two treatment groups is only undertaken if the p-values for each of the two 3-intervention tests which include a particular two intervention group are both  $p<0.05$ . For example, for interventions  $I_1$ ,  $I_2$ ,  $I_3$  and  $I_4$ , the first analysis of variance test  $I_{1234}$  assesses whether there are any differences among the four groups. If the overall test across the four groups is not significant, testing concludes and no treatment group is declared different from any other. Alternately, if that initial 4-group test is significant at the  $\alpha=0.05$  level, four separate analysis of covariance models with combinations  $I_{123}$ ,  $I_{124}$ ,  $I_{134}$  and  $I_{234}$  are tested. The comparison  $I_{12}$  is only tested if both  $I_{123}$  and  $I_{124}$  are significant at  $p<0.05$  and so forth. The closed testing procedure is chosen as the primary outcome analysis to maintain an overall study-wide  $\alpha=0.05$  while preserving power and allowing each set of interventions to be compared under pre-specified circumstances. The two primary outcomes will be analyzed separately with a total type I error probability of 0.05 for each, i.e. without an adjustment for two separate outcomes.

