Each ANCOVA model will employ White's robust (information sandwich) estimate of the covariance matrix of the model coefficients as the basis for inference [90]. This approach preserves power and protects the type 1 error probability when the homoscedastic normal errors assumptions are violated.

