## ***9.6 Handling of Missing Data***

It is anticipated that a small number of participants will require immediate rescue therapy and be unable to have the 3-month post-washout evaluation. In these cases, the primary outcome will be missing. A sensitivity analysis which includes these participants will use a conservative approach by assuming that these participants have worse function than the participants who were measured. This is implemented by ranking the observed function values from the participants who completed the washout evaluation, and assigning a lower value (or worst rank) to those with missing data [89]. The groups are then compared using a Wilcoxon rank test.

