RISE Primary Outcome Analysis Plan – Adult Medication Study

Approved by RISE Steering Committee, Sept 2017

Approved by RISE DSMB, November 2017

Often the Disposition Index (DI) – insulin sensitivity * insulin response – is used as an overall measure of beta-cell function that appropriately accounts for the reciprocal relationship of insulin sensitivity and the beta-cell's insulin response. In these analyses, the DI assumes that the product of the two variables is constant within an individual at a given time, such that changes in insulin sensitivity would be mirrored by a proportional change in the insulin response. This implies that all points along the line represent the same level of metabolic function. In many instances this relationship has been demonstrated using insulin responses to be a rectangular hyperbola (by definition, the slope of the log-log relationship equal to -1.0); however, in others this relationship has just been assumed. The power calculations for RISE were based on the DI using data provided by several investigators that used methodologies that differed from those used in RISE.

During protocol development there was thus concern that relationships underlying this constant depend on the actual measures of peptide (insulin or C-peptide) release by the beta cell. In particular, the slope of the log-log relationship between secretion and sensitivity might not be equal to -1.0 for the C-peptide measures chosen for RISE as had been observed in prior studies based on insulin measures. Therefore, the protocols specifically state that the primary outcomes would be based on two different C-peptide responses (steady state and maximal) adjusted for insulin sensitivity defined as the glucose disposal rate divided by steady state insulin (aka M/I) during the hyperglycemic clamp. However, given the likely possibility that the relationship may not be a rectangular hyperbola, the protocol did not specify details of the approach to be used for the primary outcome analysis as a decision would be based on evaluation of the baseline data.

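### The SAP's primary SUR model omits the randomisation strata, at a small cost in power, and does not carry over the protocol's sandwich covariance, a cheap safeguard that matters only under some fits

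*SAP*

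**What the plan says.** **Strata.** Protocol 3.7 randomises within clinical centre (three adult centres) and within prediabetes or diabetes. Protocol 9.1 adjusts the primary ANCOVA only for baseline β-cell function. In the SAP's sample R code the sensitivity equation is "Eq1 = log_mi ~ Treatment + log_mi_base", and the C-peptide equation likewise holds treatment and its own baseline. Diabetes status returns only as a subgroup factor in protocol 9.2.

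**Covariance.** For each ANCOVA, protocol 9.1 names White's "robust (information sandwich) estimate of the covariance matrix of the model coefficients as the basis for inference", on the ground that it "protects the type 1 error probability when the homoscedastic normal errors assumptions are violated". The SAP replaces the ANCOVA with a two-equation SUR. Its prose mentions no robust covariance. The test call, "linearHypothesis(fit12,test = 'Chisq" and so on, passes none, so it uses the fit's own model-based matrix.

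**Which arms enter a fit.** The code tests a single treatment level in each equation, "c('Eq1_TreatmentTreat2=0','Eq2_TreatmentTreat2=0", on one Month 15 data set with no subset shown. Protocol 9.1 describes separate models: "each of the four possible sets of three interventions will be compared in four separate analysis of covariance models".

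**The concern.** When randomisation is balanced within strata, differences between strata cancel out of the treatment contrast. If the strata are not in the model, those differences still sit in the residual variance. The standard error is then too large and the test loses some power.

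The covariance question is separate. The SAP changed the analysis because the log-log slope was about -0.3 instead of -1. That concerns how secretion is adjusted for sensitivity and says nothing about error variance, so it does not explain the loss of the sandwich. The SAP also says that "the protocol did not specify details of the approach to be used for the primary outcome analysis", and the protocol's sandwich sentence refers to ANCOVA models. A programmer working from the SAP could reasonably run the model-based test. With one covariance pooled over four arms, a more variable arm would have its contrasts tested against too small a variance, and contrasts among the other arms would be tested against too large a one.

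**Working it through.** **Inputs from the documents.** 56 per arm, 224 in total, and baseline to follow-up correlation 0.57 (protocol 9.3); nominal level 0.05 for each outcome (protocol 9.1). **Assumed, because the documents do not give them:** one arm's residual SD is 1.3 or 1.5 times the others; the residual correlation between the equations is -0.3; the strata explain 2, 5 or 10% of residual variance.

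**1. The plan's own power.** Simulating the closed ANCOVA procedure (40,000 runs, one arm differing from three equal arms) gives 85.7 / 83.1 / 77.7%, against 84 / 81 / 77% in Table 3. The middle row is 2.1 points high and supports the claim of at least 80%. Power is lower if the other two arms lie midway (76.0 / 72.6 / 67.6%), but that is a separate matter.

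**2. Strata: size.** With balanced strata left out, R = true variance / model variance = 1 - (share explained). The 2-df size is about exp(-5.991/(2R)):
- 2%: R = 0.98, size 4.7%
- 5%: R = 0.95, size 4.3%
- 10%: R = 0.90, size 3.6%

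Simulation agrees: 3.7–5.1% unadjusted, 5.3% adjusted.

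**3. Strata: power** (12,000 runs, 3 centres × 2 status groups, effect 0.60 in C-peptide, 2-df test):

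| Share explained | Strata act oppositely on the two outcomes | Strata act on C-peptide only |
|---|---|---|
| 2% | 86.2 → 86.5 (+0.3) | 86.0 → 86.5 (+0.5) |
| 5% | 86.8 → 87.6 (+0.8) | 86.4 → 87.6 (+1.2 from rounded values; +1.3 unrounded) |
| 10% | 87.9 → 89.3 (+1.4) | 86.8 → 89.3 (+2.5) |

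If the strata acted in the same direction on both outcomes, the gains would be 1.0 / 2.4 / 4.8 points, but the SAP reports an inverse relation. As a cross-check, an ungated 1-df pairwise test goes from 88.8% to 89.4 / 90.3 / 91.7%.

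Cost: 2 centre terms + 1 status term = 3 df per equation. A four-arm fit goes from 224 - 5 = 219 to 216.

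**4. Covariance, one four-arm fit: by hand.** With SD ratio k in one arm, the pooled variance is (3 + k²)/4. A pair with that arm has mean variance (1 + k²)/2; a pair without it has 1.
- k = 1.5: pooled 1.3125. With the arm, R = 1.625/1.3125 = 1.238, size 8.9%. Without it, R = 1/1.3125 = 0.762, size 2.0%.
- k = 1.3: pooled 1.1725. With the arm, R = 1.345/1.1725 = 1.147, size 7.3%. Without it, R = 0.853, size 3.0%.

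**5. The same by simulation** (20,000 runs, ungated 2-df test, true size in %, SD ratio 1.0 / 1.3 / 1.5 in both equations):

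| Test | Model-based | HC1 sandwich | HC3-type |
|---|---|---|---|
| Pair with the variable arm | 5.2 / 7.6 / 9.1 | 5.6 / 5.5 / 5.5 | 5.2 / 5.1 / 5.1 |
| Pair without it | 5.3 / 3.2 / 2.2 | 5.5 / 5.5 / 5.5 | 5.2 / 5.2 / 5.2 |
| Four-arm test, 6 df | 5.3 / 5.7 / 6.0 | 6.2 / 6.3 / 6.3 | 5.6 / 5.7 / 5.7 |

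If only one equation is affected, model-based size at 1.3 / 1.5 is 6.7 / 7.4% with the arm and 4.1 / 3.5% without it.

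**6. Covariance, separate refits** (SD ratio 1.3 / 1.5, variable arm listed first):

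| Month 15 numbers | Model-based | HC1 |
|---|---|---|
| 56 v 56 | 5.7 / 5.7 | 5.8 / 5.8 |
| 51 v 58 | 5.7 / 6.1 | 5.3 / 5.4 |
| 48 v 60 | 6.5 / 7.2 | 5.7 / 5.9 |
| 60 v 48 | 4.8 / 4.5 | 5.6 / 5.7 |

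In the full closed procedure with equal arms and every subset refitted, family-wise error under the global null is 5.3 / 5.7% model-based and 5.8 / 5.8% with HC1.

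**The case against.** The best defence is that silence is not repeal. The SAP labels its code as a sample, never withdraws the sandwich, and also does not restate closed testing or intention-to-treat, which nobody takes to have lapsed. Its remark that the protocol left details open follows from the doubt about the hyperbola, so it may concern only the sensitivity adjustment. This stands: a reader might infer that the SAP abandoned the sandwich, but the documents show only that it is not carried over.

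A reader might also infer that the primary analysis runs at 7–9% type I error. The documents do not support that. Those figures belong to ungated pairs from one pooled four-arm fit, which no text specifies. One coefficient label does not establish such a fit, because a two-arm refit can print the same label. Protocol 9.1 implies separate models, where the working shows little harm. No arm variances are given, and both outcomes are logged, which may narrow differences in spread.

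The unequal-size cases are also stretched. With 255/4, about 64 randomised per arm, 48 v 60 means about 25% missing in one arm and 6% in the other. Protocol 9.3 plans for 10%, and protocol 9.6 expects only a few participants to need rescue and "be unable to have the 3-month post-washout evaluation". The distortion can run either way.

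Finally, White's estimator without a small-sample correction is not free. In 10,000 runs with equal variances, the four-arm test had size 6.7%, against 5.2% model-based. Protocol 9.1 does not ask for an HC3-type form; that is a suggestion made here.

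On the strata, baseline-only adjustment is a legitimate prespecified choice, and leaving the strata out does not invalidate the test. What remains is that the power is available at almost no cost.

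**Conclusion.** Two modest improvements are worth making; neither corrects a demonstrated error.

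**Strata.** Omitting them is conservative. It forgoes about 0.3 to 2.5 points of power if they explain 2–10% of residual variance. That share is an assumption. It would be wrong to infer a false-positive risk: the unadjusted test runs at or below its adjusted size.

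**Covariance.** The SAP does not carry over a safeguard that the protocol made the basis for inference, and it gives no reason. The safeguard matters if pairs are read from one four-arm fit and one arm is 1.3–1.5 times as variable: about 7–9% for pairs with that arm and 2–4% for the others, brought back to about 5–6% by the sandwich. With separate, equal-sized refits there is no material distortion. A small one, in either direction, appears only if arm sizes at Month 15 differ. The arm SDs and the residual correlation are assumed.

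**What to change.** 1. Add clinical centre and prediabetes/diabetes status to both SUR equations. Both factors are known for everyone randomised. The cost is 3 degrees of freedom per equation.

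2. Supply a heteroscedasticity-consistent covariance, stacked over the two equations, to the joint 2-df test and to the higher-order tests of the closed procedure, or state why the protocol's safeguard is not kept. An HC3-type correction is preferable, as a suggestion beyond what protocol 9.1 requires. With equal variances it leaves the pair test at 5.2% and moves the four-arm test from 5.3% to 5.6%. HC1 raises the four-arm test to 6.2%, and the uncorrected form raises it by about 1.5 points (6.7% v 5.2%).

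3. While editing, add a clause naming the arms that enter each fit. This is only missing detail, but it settles whether the four-arm case can arise.

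The whole change is SAP wording and a few lines of code, with no new data.
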